5.5.2 REPEATED SCREENING VISITS (VISIT 0/R1 OR VISIT 0/R2)

In some circumstances a repeated screening may need to be scheduled. Examples include, but are not limited to:

- 1. Incomplete information available at time of screening to determine eligibility (e.g. current lens brands worn, history from current eye care practitioner etc.);
- 2. Study procedures unable to be completed in time scheduled for visit;
- 3. Study products not available at the time of the screening visit;
- 4. A transient health condition which may affect the eye(s) (e.g. a common cold, active allergies, fatigue etc.);
- 5. The short-term use of medications (e.g. antibiotics, antihistamines etc.);
- 6.

The maximum total number of screenings permitted will be 2, the initial and one repeat screening visit.

5.5.3 VISIT 1-0 DISPENSE LENS TYPE #1

This visit may or may not be subsequent to the screening visit, depending on lens availability but will occur no later than 28 days after Visit 0. If this visit occurs on a different day as the screening visit, participant should attend this visit wearing spectacles.

The study procedures are outlined below:

- 1. Confirm participant's health and medications are unchanged.
- 2.
- After a minimum 5-minute washout time after fluorescein insertion, participant to insert Lens type #1 according to the randomization table. Ensure that both investigator and participant are fully masked to the study lens type.

- Provide and explain to participant the subjective at-home rating forms to be completed on Day 6 (Note: Day 1 is the day after the dispensing visit). Fill in the days and dates on these forms.
- The participant will receive lens supply and will be instructed to wear the lenses for at least 8 hours a day, 7 days a week.
- 9. Visit 2-0 will be scheduled 7-10 days after Visit 1-0.

5.5.4 VISIT 2-0, 1-WEEK FOLLOW-UP LENS TYPE #1, DISPENSE LENS TYPE #2

Participants will be asked to insert Lens type #1 at least 2 hours prior to the visit. This visit will occur 7-10 days (inclusive) after visit 1-0.

The study procedures are outlined below:

- 1. Confirm participant's health and medications are unchanged.
- 2. Review 'at-home' ratings for completeness and legibility.

3.		
4.		
7.	The participant will remove the lenses.	
8.		

- 9. Continue with the lens dispense for Lens type #2 as described in visit 1-0 starting at point #3 to #8.
- 10. Visit 3-0 will be scheduled 7-10 days after Visit 2-0.

5.5.5 VISIT 3-0 1-WEEK FOLLOW-UP LENS TYPE #2

Participants will be asked to insert Lens type #2 lenses at least 2 hours prior to the visit. This visit will occur 7-10 days (inclusive) after visit 2-0.

The study procedures are outlined below:

- 1. Confirm participant's health and medications are unchanged.
- 2. Review 'at-home' ratings for completeness and legibility.

3.			
4.			
5.			

The participant will remove the lenses.

9.

10. Continue with Study Exit.

5.5.6 STUDY EXIT

The study exit form will be completed when a participant exits the study. This form will be completed either at study completion, or if the participant is discontinued from the study at another time. A study exit form must be completed for all participants who have taken a study ID number. If in the opinion of the investigator post-study follow-up visits are required, the exit form will be completed after the last follow-up visit.

After the exit assessments have been completed, the participant and investigator will complete the study completion and remuneration forms. At this time the participant will be considered as having exited the study.

5.5.7 UNSCHEDULED VISITS

An unscheduled visit is defined as an interim visit requested by the participant or investigator due to an unanticipated problem. Data recorded at these visits will be entered into the database. Only relevant and applicable unscheduled visit information will be included in the final report as deemed necessary.

5.6 STUDY PROCEDURES

Table 4 summarizes the procedures conducted at each visit.

	0 Screen & Fit of study Lenses	1-0 Dispense Lens type #1	2-0 1-week follow-up Lens type #1 dispense Lens type #2	3-0 1-week follow-up Lens type #2 and Exit
Consent process	x		5 8 1	
Subject age & sex	x			
CL history and/or lens wear schedule	x	-	x	x
	x		x	x
Health & medication	x	x	x	x
Review any problems with eyes/study lenses		x	x	x
	x			X (or with subj. refraction from V 0)
	x	4		
	x			
	x			
Dispense study CLs		x	x	·
	x	x	x	x
	x	x	x	x
			x	x
				x
Issue 'at-home' subjective ratings		X	x	
Collect & review 'at home' ratings			x	x
	X	x*	x	x
Study Exit				x

Table 3: Summary of procedures to be conducted at scheduled visits

* Not required if visit concurrent subsequent to previous one.

EX-MKTG-148 SUN Protocol v1.5 23Feb2023

6 MONITORING PROTOCOL ADHERENCE

Adherence to study visit windows, lens wearing schedule, and time windows around other data collection points (i.e. subjective ratings) will be monitored by CORE. Deviations from the study plan as described in the protocol will be reported in the study report. As described in Section 13.4, major protocol deviations will be reported to the Sponsor and Sterling Institutional Review Board within 10 days of becoming aware of them (as per Sterling Institutional Review Board guidelines).

7 POTENTIAL RISKS AND BENEFITS TO HUMAN PARTICIPANTS

There may be no direct benefits to the subjects in this study. Participation in a study may contribute to scientific research information that may be used in the development of new contact lens products. The subjects will receive an examination of the front part of their eyes and may have the opportunity to try a different type of soft contact lenses and/or different lens care products at no cost to them. The contact lens materials used in this study are commercially available as daily wear. This study will investigate participants' wearing schedule intended for daily wear (NOT extended wear), similar to the average wearing time of 10-16 hours for daily wear lenses.

All lenses used in this study are IDE exempt under 21 CFR 812.2(c)2.

The habitual lens and the two study contact lens types will be worn as per their approved use; on a daily wear, daily disposable basis. When contact lenses are worn on a daily wear basis there is a small risk of an adverse event compared to not wearing contact lenses. When contact lenses are worn on an extended wear basis, there is a significantly increased risk of an adverse reaction compared with wearing contact lenses on a daily wear basis.

Adverse events and/ or complications in daily wear of soft contact lenses can occur (eg: inflammation and infection). Complications that may occur during the wearing of contact lenses

include discomfort, dryness, aching or itching eyes, excessive tearing, discharge, hyperemia and variable or blurred vision. More serious risks may include pain, photophobia, iritis, corneal edema or eye infection. Although contact lens-related infections are very infrequent, the possibility does exist. The incidence of infection due to day-wear soft lenses is 0.035%. Almost always an infection will occur only in one eye. This risk is assumed by 35-million Americans who currently wear contact lenses and only current soft lens wearers will be recruited for this study.

A dye (fluorescein) normally used for eye examinations is being used in this study. Although rare, it is possible to have an allergic reaction to the dye. Participants will be asked if they have a known allergy or sensitivity to fluorescein.

The assessments conducted in this study are routine clinical procedures and they include autorefraction, auto-keratometry, visual acuity, anterior ocular health assessment, and contact lens fitting will be used. In addition, high magnification imaging of the lens fit may be made using 35 mm or digital cameras. Patients will be monitored frequently until the end of the study to reduce the occurrence of adverse or potential adverse events. Patients will be given instructions from their investigator regarding early symptoms and signs of adverse events.

8 ADVERSE EVENTS

See CORE SOP012 for a description of all adverse events, including management and reporting. An 'adverse event' refers to any undesirable clinical occurrence in a participant, whether it is considered to be device-related or not. Adverse events (AE) may be classified as 'unanticipated adverse device effects,' 'serious adverse events,' 'significant adverse events,' or 'non-significant adverse events,' as defined below, Table 5.

A number of conditions may result in temporary suspension until resolution. These include corneal infiltrates, corneal staining, limbal injection, bulbar injection or tarsal conjunctival abnormalities.

Classification	Definition
Serious Adverse Event	Those events that are life-threatening, or result in permanent impairment of a body function, or permanent damage to a body structure or necessitate medical (therapeutic) or surgical intervention to preclude permanent impairment of a body function or permanent damage to a body structure.
Significant Adverse Event	Those non-serious adverse events that occur with contact lens usage that are not sight-threatening but are usually symptomatic and may warrant therapeutic management and /or temporary or permanent discontinuation of contact lens wear.
Non-Significant Adverse Events	Those less severe non-serious adverse events that occur with contact lens usage that are not sight-threatening, may or may not be symptomatic and may warrant palliative management, such as ocular lubricants or temporary interruption of contact lens wear.
Unanticipated Adverse Device Effect	Adverse events in a study that were not previously identified in the protocol in terms of nature, severity, or degree of incidence. An Unanticipated Serious Adverse Device Effect is an unanticipated adverse event that is serious in nature and caused by or associated with the device and is considered reportable.

AE classification, coding (for reporting to the sponsor) and reporting details, plus examples, are provided in Table 6.

Table 5: Contact lens adverse even	classification,	coding and	reporting guide
------------------------------------	-----------------	------------	-----------------

Code	Condition	Reporting			
Serious Adverse Events					
01	Presumed infectious keratitis or infectious corneal ulcer				
02	Permanent loss of \geq 2 lines of best spectacle corrected visual acuity (BSCVA)	-			
03	Corneal injury that results in permanent opacification within central cornea (6mm)	For all serious AEs:			
04	Uveitis or Iritis (e.g. presence of anterior segment inflammation as described in ISO 11980, Annex B)	Notify sponsor as soon as possible,			
05	Endophthalmitis	within 24 hours;			
06	Hyphema	ORE reporting			
07	Hypopyon	hours as per			
08	Neovascularization within the central 6mm of cornea	requirements			
00	Other serious event				
Significant Adverse Events					

11	Peripheral (outside central 6mm), non-progressive, non-infectious ulcer			
12	Symptomatic corneal infiltrative event			
13	Superior epithelial arcuate lesions (SEALs) involving epithelial split			
14	Corneal staining ≥ dense coalescent staining up to 2mm in diameter (e.g. moderate, ISO 11980 grade 3)	Notify sponsor as soon as possible,		
15	Corneal neovascularization ≥ 1.0mm vessel penetration (e.g. ≥ ISO 111980 Grade 2), if 2 grade change from baseline	days; ORE reporting as per		
16	Any temporary loss of ≥ 2 lines BSCVA for ≥ 2 wks	requirements		
17	Any sign and/or symptom for which participant is administered therapeutic treatment or which necessitates discontinuation of lens wear for \geq 2 weeks			
10	Other significant event			
Non-significant Adverse Events				
21	Conjunctivitis (bacterial, viral or allergic)			
22	Papillary conjunctivitis if ≥ mild scattered papillae/follicles approximately 1mm in diameter (e.g. ISO 11890 Grade 2), if 2 grade change from baseline	Notify sponsor as		
23	Asymptomatic corneal infiltrative events	within 5 working		
24	Any sign and/or symptom for which temporary lens discontinuation for > 1 day is recommended (if not already classified)	reporting as per requirements		
20	Other sign and/or symptom warranting classification as a non-significant adverse event			

8.1 NORMAL OR ADAPTIVE SYMPTOMS

Transient symptoms such as end-of-day dryness, lens awareness, itching or burning or other discomfort may occur with contact lens wear and may occasionally reduce wearing time. These are not reported as adverse events unless in the investigator's opinion they are unexpected in nature, severe or have a high rate of occurrence.

8.2 PROCEDURES FOR ADVERSE EVENTS

Treatment of an adverse event will depend on its nature and severity. Based on the clinical judgment of the investigator the participant may be managed at the practice, or referred to another eye care practitioner for treatment. The investigator will attempt to determine whether the reaction is related to the test device or a result of other factors. An adverse event form will be completed

for each adverse event. If both eyes are involved, a separate adverse event form will be completed *for each eye*. Whenever possible, the adverse event will be photo-documented.

Expenses incurred for medical treatment as part of study participation will be paid by the sponsor (bills and prescription receipts kept). The participant must be followed until resolution or no further change is anticipated and/or referred for further care with the appropriate health care professional and/or recorded as being under appropriate health care as per investigator's discretion. A written report will be completed indicating the subsequent treatment and resolution of the condition.

8.3 REPORTING ADVERSE EVENTS

All potential Serious and Unanticipated Adverse Device Effects that are related or possibly related to participant's participation will be reported to CORE's lead study coordinator (details below) and also to the sponsor (details below) within 24 hours of the investigator becoming aware of the event. The site's Principal Investigator will also report the event to Sterling IRB within 10 days of becoming aware of the Serious or Unanticipated event, using the Reportable Events Form. All fatal or life-threatening events will be reported immediately to the IRB, CORE and the sponsor.

Adverse Events will be reported to CORE's lead study coordinator and the sponsor as soon as possible, but no later than 5 working days after the occurrence. Each site's Principal Investigator will report the event to the IRB as per IRB requirements (by fax, mail/delivery, phone, or email).

Details of all adverse events will be included in the study report.

EX-MKTG-148 SUN Protocol v1.5 23Feb2023

9 DISCONTINUATION FROM THE STUDY

Participants may be discontinued at the discretion of the investigator or sponsor in consideration of participant safety or protocol compliance, or at discretion of the participant. Participants discontinued from a study will be reimbursed per visit for their active involvement in the study (including the initial screening visit and all lens fitting visits). Upon discontinuing, a participant will be offered the option of their data being withdrawn from future statistical analysis. The following is a list of possible reasons for discontinuation from the study:

- Screening failure: Participants will be discontinued if they do not meet the inclusion and exclusion criteria outlined in section 5.2.3.
- Unacceptable performance with products to be used in study: Participants may be discontinued if they are unable to achieve acceptable comfort and /or vision with the study products.
- Positive slit lamp finding: Participants may be permanently discontinued from the study depending on the severity of the condition and on the judgement of the investigator.
- Adverse event: If a participant experiences an adverse event during the study they may be discontinued based on the clinical judgement of the investigator.
- Symptoms: If the participant has persistent symptoms they may be discontinued based on the clinical judgement of the investigator.
- Disinterest, relocation or illness: The participant may choose to discontinue due to reasons within or beyond their control.
- Violation of protocol or non-compliance: The participant will be discontinued if they are unable or unwilling to follow the protocol specified visit schedules and/or study procedures.
- Instillation of topical ocular medication: The participant will be discontinued if they elect to use a topical ocular medication during the study unless that topical ocular medication is prescribed for a limited duration (less than two weeks) to treat a transient condition; in this case the participant may remain an active participant (at the discretion of the investigator) after stopping topical ocular medication following resolution of the ocular condition).

- Lost to follow-up: The participant will be discontinued if they cannot be contacted and do not return to complete the final study exit, and if the investigator has made a reasonable effort to contact the participant for a final study visit.
- Premature termination of the study by the sponsor, CORE or Sterling IRB.

A discontinuation form, stating the reason for discontinuation will be completed, which requires the signatures of both the participant and the investigator except where the participant is lost to follow-up in which case only the signature of the investigator is required.

When a participant choses to discontinue from the study they will be given the opportunity to withdraw their data from the statistical analysis. This choice will be captured on the discontinuation form.

All discontinuations including their reasons will be included in the final report.

10 DEVICE MALFUNCTIONS

A device malfunction means the failure of the device to meet its performance specification or otherwise perform as intended. Any defective lens that is *likely* to cause or contribute to a *Serious Adverse Event* should be reported to CORE and the sponsor **within 24 hours** of the investigator becoming aware of the malfunction. Sterling IRB would also be notified within 24 hours of any device malfunction that may contribute to a *Serious Adverse Event*.

Other defective lenses should be reported to CORE as soon as possible (usually in weekly study updates).

This clinical study will also ascertain satisfaction or preference with subjective attributes such as comfort, vision, or lens handling. Responses to these subjective questionnaires will not be considered as complaints or device malfunctions.

11 STUDY COMPLETION AND REMUNERATION

At the last scheduled protocol visit a study completion form will be completed, which requires the signatures of both the participant and the investigator. Participants will also be provided with a letter of appreciation.

Once their involvement in the study is complete, participants will be informed about receiving feedback following study completion in the Letter of Appreciation.

Participant remuneration will be paid as per site contract.

12 STATISTICAL ANALYSIS AND DATA MANAGEMENT

12.1 STATISTICAL ANALYSIS

All data will be analyzed by CORE at the University of Waterloo. Unmasked data analysis will be conducted using Statistica 10, Statsoft or other suitable software. Descriptive statistics will be provided on demographic data (age, gender, refractive error distribution, etc.). Table 7 lists the primary and other outcome variables and anticipated statistical procedures.

Visual acuity results will be converted to LogMAR for analysis purposes.

Comparisons will be made between the study lenses for the variables measured at the 1-week visits. Additionally the subjective ratings completed on days 1, 3 and 6 with each study lens will be compared for differences and equivalence. A binomial test will be used to analyze the results for the count data of subjective preferences and experience responses. Where relevant, the number of "no preference" responses will be evenly distributed to the two options on the basis they would be equally likely to choose either.

For assessments conducted for each eye separately, the right eye will be used for analysis. If a general difference is found (paired t-test / Wilcoxon matched pairs) between OD and OS, a comment will be provided

Where appropriate, data may be presented as both mean and as counts by 'bucket' groups.

Additional analysis may be conducted

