5 MATERIALS AND METHODS

5.1 STUDY DESIGN

5.1.1 OVERALL DESIGN

This study is a prospective, bilateral eye, double-masked, randomized, 1-week cross-over, dailywear design involving two different daily disposable lens types. Each lens type will be worn for approximately one week, during which participants record their subjective lens-wear experience on three different days.

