5.1.2 RANDOMIZATION

A randomization schedule will determine the order of CONTROL and TEST CL wear for the first/second week for each participant. Participants will be randomized immediately prior to their first lens dispense.

This randomization schedule will be generated for each site using a web-based program: (for example www.randomization.com). The lens type that will be worn during the first week is called "Lens type #1", the lens type dispensed for the second week is called "Lens type #2". The final study randomization schedule will be generated by CORE's Database Administrator and provided to the unmasked research assistants at each site.

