5.1.3 MASKING

This study will be double masked i.e. participants and investigators will be masked to the lens type dispensed. In order to achieve this, unmasked research assistants will determine the lens order according to the randomization schedule (see section 5.1.2) and will over-label the lens packages/foils prior to dispense by placing strongly adhesive stickers on the packages/foils to mask the participant and investigator to the lens brand. At the fitting visit both lens types will be fit, but only the participant can be masked to the lens type during this process because the investigator needs to know which type is being fit in order to follow the fitting guide when making changes to the lens. During the lens wear phases both investigators and participants will be masked.

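### Section 12.1 plans an unmasked analysis by the organisation that holds the randomisation schedule, with some analysis choices still open; coding the lenses A and B would be a cheap improvement

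*Combined protocol and SAP*

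**What the plan says.** **Who analyses, and in what state.** Section 12.1: "All data will be analyzed by CORE at the University of Waterloo", followed by "Unmasked data analysis will be conducted using Statistica 10, Statsoft or other suitable software".

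**Who holds the schedule.** Section 5.1.2: "The final study randomization schedule will be generated by CORE's Database Administrator and provided to the unmasked research assistants at each site". CORE also enters the data (12.2) and reviews and queries them (14).

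**Who is masked, and when.** Section 5.1.1 describes the study as "prospective, bilateral eye, double-masked, randomized, 1-week cross-over". Section 5.1.3 defines the term: "This study will be double masked i.e. participants and investigators will be masked to the lens type dispensed". It adds: "During the lens wear phases both investigators and participants will be masked". Analysts are not mentioned.

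**What is left open.**
- Section 5.5: visits outside their windows are protocol deviations, and the suitability of the data for the analysis population is assessed at the end of the study. No criteria are given.
- Section 12.1: no-preference answers are divided evenly between the lenses where relevant. The items are not listed there.
- Section 12.1: "Where appropriate, data may be presented as both mean and as counts by 'bucket' groups". No bucket limits are given in the visible text.
- Section 12.1: additional analysis is allowed without further definition.

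The visible text describes no coded labels, no separation of the analyst from the schedule, and no point at which these choices are settled before lens identity is known.

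**The concern.** Sections 2 and 3 set the sponsor's marketed lens (CONTROL) against a competitor's recent launch (TEST). The outcomes include participants' own ratings and preferences. Masking protects how those answers are given. It does not protect decisions taken afterwards about which records count, how undecided answers are handled and what is displayed. If the person deciding can see which brand gains, a reader of the report cannot rule out that the brand influenced the decision. What is at stake is the credibility of the secondary, preference and descriptive findings, and of the population on which everything is analysed. The validity of the trial as a whole is not in question.

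**Working it through.** **1. The plan's own figure.** Section 5.3.1 uses a two-sided paired t-test with difference 10, SD of paired differences 24.2 and alpha 0.05. Power is P(|T| > t(0.975, n−1)), where T is noncentral t with n−1 degrees of freedom and noncentrality (10/24.2)·√n.

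| n | Stated power | Recomputed |
|---|---|---|
| 48 | 0.800662 | 0.8007 |
| 54 | 0.846406 | 0.8464 |
| 64 | 0.902344 | 0.9023 |

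The figures reproduce. None of the inputs depends on whether the analyst sees brand names or the letters A and B, so masking the analyst leaves n, alpha and power unchanged.

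**2. Is there a contradiction?** Set 5.1.3 beside 12.1. The first masks participants and investigators, in particular during lens wear. The second unmasks the analysis. They concern different people at different stages and are compatible.

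**3. What each open choice can do.**

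*Deviation data (5.5).* This decision can reach the primary result. The Day 6 ratings come back at the follow-up visits (5.5), and section 6 monitors time windows around ratings as well as visits. Leaving participants in or out changes the paired differences being averaged. The documents give no expected number of deviations, so the effect cannot be sized.

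*Splitting undecided answers (12.1).* Let a and b be the counts preferring each lens and t the number undecided.
- Dropping the undecided gives approximately z = (a − b)/√(a + b).
- Splitting them evenly gives approximately z = (a − b)/√(a + b + t).

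The numerator is the same and the second denominator is larger, so splitting weakens the evidence and never reverses it. With assumed counts of 30, 14 and 20 undecided (total 64):
- Dropping: 16/√44 = 2.41; exact binomial test of 30 v 14, p = 0.023.
- Splitting: 16/√64 = 2.00; exact binomial test of 40 v 24, p = 0.060.

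The choice can therefore change the conclusion for an item. Does having the choice inflate the error rate? I computed exact binomial tests for a total of 64, no true preference and every even t from 2 to 30. Splitting was never significant when dropping was not. The false-positive rate of taking whichever is significant therefore equalled that of always dropping, and was at most 4.9%. There is no inflation above 5%.

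*Buckets (12.1).* The visible text attaches no test to the bucket counts. The risk is selective display, which has no false-positive rate.

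*Additional analyses (12.1).* These are open-ended. The documents give no number or form, so there is nothing to calculate.

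**4. What unmasking itself adds.** An analyst who always reports the most favourable of several versions has the same two-sided error rate whether the lenses are called A and B or by brand. What sight of the brand adds is direction: choices can consistently favour one product. Coding removes that. Settling the choices in advance removes the choice itself. The two measures do different jobs, and both are needed.

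**The case against.** The strongest reply is that nothing here departs from what was promised. Double masking is defined without the analyst, and 12.1 openly discloses the unmasked analysis. The analysis is done at a university and not by the sponsor's staff. The primary outcome is one variable on one day, rated by masked participants, with a paired t-test as the basis of the sample size. Table 7, which lists outcomes and procedures, is not in the text available here and may settle more than 12.1 shows. The data management plan promised in 12.2 may also bear on data handling and personnel. All of this stands, and it limits the point to a minor one.

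Three stronger readings are tempting and are not supported:
- *That the plan contradicts its double-masked label.* Section 5.1.3 rules this out.
- *That the preference and bucket results carry an inflated error rate.* The split-or-drop choice does not raise it, the buckets have no stated test, and any gain from picking the best version would be the same under coded labels.
- *That the person who makes the schedule also analyses the data.* The documents place both tasks in one organisation and do not say they fall to one person.

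What remains is that 12.1 specifies the unmasked analysis outright, and that neither 5.5 nor the visible text of 12.1 settles the open choices before lens identity is known.

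**Conclusion.** The point holds as a cheap improvement. Unmasked analysis within the organisation that holds the schedule, combined with choices deferred until the data are in, leaves room for decisions guided by brand. The exposure lies mainly in secondary and descriptive results and in the inclusion of deviation data. Apart from that inclusion decision, the Day 6 comparison is little exposed. No numerical size can be attached: the documents do not give the number of deviations, of undecided answers or of added analyses, and there is no evidence that bias will occur. The conclusion assumes that no text outside what is visible, such as Table 7 or the data management plan, already provides for coded analysis or settles these choices.

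**What to change.** In section 12.1, replace the unmasked analysis with analysis of the locked dataset in which the Database Administrator has labelled the lenses A and B. Before the code is released, settle and date:
- which deviation data enter the analysis population, with reasons;
- the preference items whose undecided answers are split;
- any bucket limits, and the variables they apply to.

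Complete the planned comparisons under the coded labels, then open the code. Label any analysis added afterwards post hoc. Add a cross-reference in 5.5 so that the end-of-study assessment of deviations falls before decoding.

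The cost is a few sentences in the plan, one recoded variable, a short lock-and-decode step and a dated record of the decisions. The Database Administrator already generates the schedule, so no new role is needed. Sample size, visits and data collection do not change.
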